### 5/ Subject Enrollment and Randomization Procedures

If the patient meets the P/F ratio criterion for randomization (from ABG or imputed from SpO2), they will be randomized simultaneously with enrollment. Otherwise their P/F ratio will be followed until it is <200 or they exit the 48h ARDS window. If the patient meets the P/F ratio criterion within the ARDS window, mark the “Yes” box about randomization on line 12, otherwise check the “No” box. If the patient is randomized, collect the baseline blood sample, obtain the treatment assignment using the on-line assignment tool, enter the randomization date and time on line 14 and the treatment assignment on line 15. Once Randomized, baseline information will be recorded on the Baseline Data CRF and, if assigned to the Therapeutic Hypothermia arm, sedation, NMB, and cooling will begin as soon as possible.

### 6/ Study Visit Schedule/Schedule of Events (see Gantt chart below)

DAYS	-2	0	1	2	3	4	7	8-27	28	ICU DC	Hospital DC	60	90
Screening data, consent, enrollment, monitor for randomization	X												
Pregnancy test (F)		F											
Randomization, baseline data, start assigned temperature management		X											
Q2h vital signs (e.g. SpO2, mean airway pressure, core temperature)		X	X	X	X	X	X						
Temperature management protocol		X	X	X	X								
ABGs		A	A	A	A	A	A						
Basic metabolic panel, CBC (times per day)		2	2	2	2	2	1						
Blood sugars (times per day)		4	4	4	4	A	A						
Research blood sample collection		X	X	X	X	X	X						
Ventilator and respiratory parameters	X	X	R	R	R	R	R						
Fluid management		X	X	X	X	X	X						
NMB status	X	X	X	X	X	X	X						
Medication review (pressors, steroids, inhaled vasodilators)		X	X	X	X	X	X						

Monitor for AEs		X	X	X	X	X	X	X	X	x	x	X	X
Calculation 28-day VFDs, ICU-FDs									X				
MOCA										X	X		
Assess Vital and functional status		X	X	X	X	X	X	X	X	X	X	X	X

X = Required (time not specified)

A = When Available

R = Measured during daily reference measurements (0600-1000). When more than one value is available, the value obtained closest to 8 a.m. will be recorded.

F = Required on females of reproductive age.

## 7/ Study Measurements

Both arms will receive the same standard of care procedures listed below.

### 7.1/ Vital signs

Heart rate, Blood Pressure, Respiratory rate, Pulse oximetry, Core temperature (esophageal or rectal, temperature sensing bladder catheters, or pulmonary artery catheters, if present). All vital signs will be measured by standard of care and recorded as per study data collection requirements.

### 7.2/ Ventilatory and respiratory parameters

Ventilatory and respiratory parameters ( Peak Airway Pressure (Ppeak), Airway Plateau Pressure (Pplat), Positive End Expiratory Pressure (PEEP) and Mean Airway Pressure ( $P_{\overline{aw}}$ ) will be obtained from standard of care mechanical ventilation record. Driving Pressure is calculated as the difference between airway plateau pressure and end-expiratory pressure (Pplat – PEEP) during a breath without spontaneous ventilator effort and Oxygen saturation index (OSI). This will be calculated as the product of mean airway pressure, fraction of inspired oxygen, and 100, divided by pulse oxygen saturation ( $P_{\overline{aw}} \times FIO_2 \times 100/SpO_2$ ) will be calculated and recorded per study data collection requirements.

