### 1.2/ Study Aims and Objectives

We will conduct the CHILL-pilot single-center RCT of TH in patients with COVID-19 and ARDS with P/F < 250 to address the following specific aims:

1. **Aim 1: Analyze the safety and feasibility and the potential lung protective effect of treating patients with COVID-19 infection and ARDS with P/F < 200 with mild TH (core temperature 34°-35°C) + NMB for 48h compared with controls receiving standard temperature management.** We expect the TH-treated group to achieve targeted temperature within 4h of randomization and to maintain TH for 48h without significant increase in serious adverse effects compared with the control arm.
2. **Analyze the potential lung protective effect of mild TH (core temperature 34°-35°C for 48h) and NMB in patients with ARDS and P/F < 200 compared with controls receiving standard temperature management.** We expect the TH-treated group to trend toward having more 28-day VFDs (primary) and 28-day ICU-FDs, and improved day-3 driving pressure and OSI than the controls.
3. **Evaluate the effects of TH on systemic inflammation and extrapulmonary organ dysfunction.** We expect the treated group to have reduced levels of proinflammatory mediators and lower Sequential Organ Failure (SOFA) scores than controls.

The proposed pilot study will determine whether we can safely include patients with COVID-19 and ARDS in our larger Phase IIb trial of TH and NMB in patients with ARDS. It will help us determine whether the 48h duration of cooling is sufficient.

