## 8/ Study Interventions

### Temperature management:

1. Therapeutic Hypothermia Arm: The participating ICUs share an established institutional protocol for NMB and TH, which will facilitate rapid mobilization of treatment following randomization. Sedation will be adjusted to achieve a RASS -4 score and cisatracurium (Nimbex™) will be initiated and adjusted to the lowest rate that achieves nerve stimulation response of 2 twitches in train-of-four monitoring, reduction in ventilator dyssynchrony to acceptable levels, and elimination of shivering. NMB will be continued through the rewarming phase at least until core temperature reaches 35.5°C (~54h total time). Note that if the supply of Nimbex in the Clinical Pharmacy is insufficient to treat the subject, a supply of study-only Nimbex is available in the Investigational Drug Service Pharmacy.

Since the objective of CHILL-pilot is to test the effectiveness of cooling to a target temperature rather than the performance of a specific cooling device, patients in the TH arm will be cooled using one of the institution's two FDA-approved surface cooling devices, Blanketrol II cooling blankets or Arctic Sun™ cooling system. Core temperature will be reduced to 34°-35°C as quickly as possible and TH maintained for 48h. Patients will then be rewarmed to 36°C by 0.3°C/h and the cooling device removed. Post-cooling fever suppression is not part of the CHILL-pilot protocol. Cooling parameters were selected to optimize risk:benefit ratio. The criteria for early termination of hypothermia are persistent severe bradycardia (heart rate < 30 associated with mean arterial pressure <65 without vasopressor agents), uncontrolled bleeding, and intractable ventricular arrhythmias.

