### Placing the order to initiate hypothermia:

- Order sedation to RASS >-4 and Nimbex to achieve 2 twitches on train-of-four testing.
- Enter UMMC MED-CC Hypothermia Following Arrest Supplemental order set in Epic with the following modifications:
  - i. De-select: Capnography, CVP monitoring, SvO2 monitoring, NPO, Bair Hugger, Maintain MAPBP > 80 mmHg, Document Water temperature, CXR, sodium chloride 0.9% bolus, fentanyl, and vecuronium, cisatracurium.
  - ii. Under Chemistry, select Comprehensive Metabolic Panel
  - iii. Modify Hyper/Hypothermia order by changing stop date from 24h to 48 h and changing comments to: "Lower patient's temperature to **34 – 35C** as quickly as possible per protocol. Maintain **core temperature between 34 and 35C for 48 hours**. AT **48 hrs** after the initial cooling, re-warm patient no faster than **0.3** degree C per hour to **36C**." Delete "Then maintain ≤ 37C for 48 hours." (Changes from Epic order set are underlined and bolded.) These instructions have been added to the Randomization CRF.

2. Usual Temperature Management Arm: Controls will receive sedation and NMB as clinically indicated to achieve synchrony with the ventilator. During the 54h post-randomization period (corresponding with cooling and rewarming in the TH arm), acetaminophen will be given for core temperature  $>38^{\circ}\text{C}$  and surface cooling initiated for core temperature  $>38.5^{\circ}\text{C}$  and adjusted to maintain temperature  $\leq 38^{\circ}\text{C}$ . If patients are hypothermic (core temperature  $<35.5^{\circ}\text{C}$ ), surface warming will be initiated to restore core temperature to  $37^{\circ}\text{C}$ . Following the 54h treatment period, temperature management in both arms will be directed by the ICU team.

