- Indicate whether the patient received an inhaled vasodilator since randomization by checking the appropriate “Yes/No” box on line 23. If “Yes,” indicate which agent(s) by checking the appropriate box(es) and the total hours one or more of the agents were administered in the indicated field.
- Indicate if the patient received vasopressor support at any time since randomization by checking the appropriate “Yes/No” box on line 24. If “Yes,” check the box next to each of the agents that was received, the highest infusion rate (and units) received, and the total hours receiving any vasopressor support. If “no” skip to question 25.
- Beginning on line 25, record the highest and lowest values for each indicated laboratory value since randomization. If there is only one value, record it in the lowest value field, and click the single value box. If there are no data, check the “None” box.
- In the appropriate fields in table beginning on line 26, enter the lowest and highest blood glucose values (from finger sticks) and the date and time of the measurements for each 6-hour period since randomization. If there is only a single value, record in the “Lowest Glucose” field and check the “Single Value” box for that 6-hour time period. If there are no glucose measurements, click the “None” box for that 6-hour time period.
- Indicate all ventilator modes used since randomization by checking the appropriate boxes under line 27 and circle the mode used at 0800.
- Indicate whether the patient was extubated since randomization by checking the appropriate “Yes/No” box on line 28 and, if extubated, enter the time and date in the appropriate fields.
- Record the highest and lowest measured tidal volumes in ml during mechanical ventilation since randomization in the appropriate fields on line 29.
- Based on the EMR, estimate the total time since randomization in hours in which tidal volume exceeded 7 ml/kg during mechanical ventilation and record in field on line 30.
- Enter the highest and lowest PEEP and Mean airway pressure in cm H2O during mechanical ventilation since randomization in the appropriate fields on lines 31 and 32, respectively.
- If still intubated between 0600 and 1000 on the day after randomization, record the plateau pressure and associated PEEP measured in this time interval in the indicated fields beginning on line 33. If multiple values are present, enter the value closest to 0800. If no

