**ARDSnet Guideline Checklist (at randomization):**

Is tidal volume 5-7 ml/kg IBW?  Yes  No

Is plateau pressure ≤ 30 cm H2O?:  Yes  No

Is SpO2 between 88 and 95%?  Yes  No

Is RR < 35 BPM?  Yes  No

Is I:E ratio between 1:1 and 1:3?  Yes  No

If **NO**, ask respiratory therapist to adjust ventilator parameters to try to meet goals (might not be achievable). Date/Time of change:   /   /

**Post-change measurements:** MONTH D D Y Y Y Y TIME (0-2400)

Tidal Volume:     ml Plateau Pressure\*:   cm H2O PEEP:   cm H2O

\*Plateau pressure or equivalent (Peak Inspiratory Pressure on PS/PC, P1/high on APRB/BiVent)

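### Driving pressure is defined on a passive breath, but the plateau-pressure fields do not check for effort, and on Days 1 and 2 only the hypothermia arm is paralysed by protocol

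*Protocol*

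**What the plan says.** **Definition and source.** Protocol section 7.2 takes driving pressure as plateau pressure minus PEEP "during a breath without spontaneous ventilator effort". The same section says that the ventilator values "will be obtained from standard of care mechanical ventilation record".

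**NMB by arm.** In section 8, the TH arm is paralysed by protocol: "NMB will be continued through the rewarming phase at least until core temperature reaches 35.5°C (~54h total time". For the other arm: "Controls will receive sedation and NMB as clinically indicated to achieve synchrony with the ventilator".

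**Recording.** For Day 1, section 10.4 tells staff, if the patient is still intubated between 0600 and 1000, to "record the plateau pressure and associated PEEP measured in this time interval in the indicated fields beginning on line 33", choosing the value closest to 0800. Sections 10.5 to 10.7 repeat this for Days 2, 3, 4 and 7. The only alternatives on the daily forms are boxes for no values and for not intubated. The baseline plateau pressure (Baseline Data form, line 22) is the most recent value in the medical record before randomization. None of these entries asks whether the patient was making an effort.

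**Substitutes.** A footnote to line 24 of the Baseline Data form, which holds measurements taken after a ventilator change, accepts "Plateau pressure or equivalent (Peak Inspiratory Pressure on PS/PC" and the high pressure level on APRV/BiVent.

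**Analysis.** Aim 2 (section 1.2) names day-3 driving pressure. The SAP fits a repeated-measures mixed model to the physiological outcomes over days 0, 1, 2, 3, 4 and 7. It has no rule for non-passive, substituted or missing driving pressures.

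**The concern.** A value that meets section 7.2 and one that does not are recorded in the same box, and the chance of getting one or the other depends on the arm while protocol NMB is running. Two things can then happen on Days 1 and 2.

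- If staff enter whatever plateau is charted, which is what the forms ask, the model compares mostly passive TH readings with a mix of passive and active control readings.
- If staff apply section 7.2 and leave the box empty when there is effort, the controls who contribute are those sedated or paralysed enough to be passive, who may well be the sicker ones.

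In either case part of the arm difference on those days comes from how the reading was obtained. The SAP looks for trends toward benefit with about 10 patients per arm, so a few such readings can colour the result. Effort at the moment of the reading cannot be reliably reconstructed later.

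**Working it through.** **1. Reproduce the stated NMB duration of about 54 h.** Inputs: 48 h of cooling at 34-35°C, then "Patients will then be rewarmed to 36°C by 0.3°C/h and the cooling device removed" (section 8); for time to target, "We expect the TH-treated group to achieve targeted temperature within 4h of randomization" (section 1.2).

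Duration = time to target + 48 + (35.5 − T)/0.3, where T is the temperature at the start of rewarming.

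- T = 34, no lead-in: 48 + 1.5/0.3 = 53.0 h
- T = 35, no lead-in: 48 + 0.5/0.3 = 49.7 h
- With 4 h to target: 57.0 h and 53.7 h

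The stated 54 h lies within 49.7-57.0 h and is consistent. If NMB runs until 36°C, the longest case is 4 + 48 + 2.0/0.3 = 58.7 h. I carry 54 h with a range of 50 to 58.7 h.

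**2. Time of each reading.** The collection schedule at the end of the Screening/Enrollment/Randomization form puts Day d at 0800 on randomization day + d, and lets Day 1 last from just over 8 h to just under 32 h. Hours from randomization = 24d + 8 − (clock time of randomization).

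**3. Share of the TH arm still in the protocol NMB period at 0800.** Share = (end of NMB − earliest reading time)/24, limited to 0-100%. This assumes randomization spread evenly over the clock and no early stop.

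| Study day | Hours after randomization | Share, end at 54 h | Range, end at 50 to 58.7 h |
|---|---|---|---|
| 1 | 8-32 | 100% | 100% |
| 2 | 32-56 | (54 − 32)/24 = 92% | 75-100% |
| 3 | 56-80 | 0% | 0-11% |
| 4 | 80-104 | 0% | 0% |
| 7 | 152-176 | 0% | 0% |

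Taking the Day 3 value at 0600 instead of 0800 raises its upper limit to 19%. The asymmetry created by the protocol therefore sits on Days 1 and 2.

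**4. The Day 03 form.** Its heading and its lung-physiology block both say day 2 after randomization, against randomization day + 3 in the collection schedule. A value taken on day 2 would fall at 32-56 h, inside the NMB period. The same day-2 wording appears on the Day 04 form and in the physiology block of the Day 07 form, so it looks like carried-over template text, but it bears on the day that Aim 2 names.

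**5. Possible size, by assumption only.** The documents give no SD for driving pressure and no rate of spontaneous effort in controls.

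- *All charted values used.* Artefact = (share of controls with effort) × (shift per affected reading). Assuming shares of 20-80% and shifts of 1-4 cm H2O in either direction, it runs from 0.2 × 1 = 0.2 to 0.8 × 4 = 3.2 cm H2O.
- *Only passive values used.* If missing control values are unrelated to driving pressure, the expected shift is 0. In the worst case, the 1, 2 or 3 controls of 10 with the lowest values are the missing ones; the control mean then rises by 0.172, 0.319 or 0.458 SD (simulation from a normal distribution), in favour of TH. At an assumed SD of 4 cm H2O this is 0.7, 1.3 or 1.8 cm H2O, and it scales in proportion to the SD.

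For scale, with 10 per arm the difference detectable with 80% power at two-sided 5% is (1.96 + 0.84) × √(2/10) = 1.25 SD. The worst case above is 0.458/1.25 = 37% of that.

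**The case against.** The strongest counter-argument is that Aim 2 names day 3, and by day 3 protocol NMB is over. This stands. A reader might infer that the Aim 2 driving-pressure difference is itself a product of paralysis. On the collection schedule the documents do not support that, since 89-100% of the TH arm is past protocol NMB at the day-3 reading. What remains is that the SAP pools all days in one model without singling out day 3, and that the Day 03 form says day 2.

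A reader might also infer that the analyst has no information on effort. That is too strong. The daily forms record NMB status, stop time and return of four twitches, and staff circle the ventilator mode in use at 0800. These allow a sensitivity analysis. They are proxies, however: a sedated, unparalysed control may be passive or active, and the plateau may be read at any time from 0600 to 1000.

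Nor does the plan make one arm wholly passive and the other active. TH patients are titrated to two twitches with dyssynchrony reduced to an acceptable level, cooling can stop early, and controls may be paralysed too. The imbalance is a risk of unknown size.

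Finally, the substitution footnote covers only the line 24 post-change field, which serves the lung-protective ventilation check. It is not attached to the baseline plateau on line 22 and is not repeated on the daily forms, so it does not by itself produce a Day 1-2 difference.

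**Conclusion.** The point holds in a limited form. Section 7.2 sets a condition that the forms do not capture, and for Day 1 and most Day 2 readings the chance of meeting it differs by arm by design. That affects two of the five post-baseline days in the SAP's model. The direction and size of the effect cannot be determined from the documents; the figures in step 5 are illustrations, and the selection figures are a worst case.

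The day-3 contrast is largely free of this asymmetry. That rests on three assumptions: the randomization day + 3 timing is the one followed, NMB is not often continued beyond the protocol period in the TH arm, and readings are taken near 0800. Day 3 is not free of effort-affected readings in both arms, which the same tick would identify.

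Severity is minor. The primary outcomes are cooling performance and safety, and driving pressure is one of several secondary outcomes in 20 patients. The change is still worth making, because the missing information can be collected only at the bedside.

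**What to change.** **Forms**
- Add *spontaneous effort at measurement: Yes/No* beside plateau pressure on the baseline and Day 1, 2, 3, 4 and 7 forms.
- Code any line 24 substitute as not a plateau for the driving-pressure outcome, and keep it for the ventilation adherence check.
- Reconcile the day-2 wording on the Day 03 form (and on the Day 04 and Day 07 forms) with the collection schedule.

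**SAP**
- Driving pressure uses no-effort values only, as section 7.2 defines it.
- Day 3 is the between-arm contrast; Days 1 and 2 are descriptive.
- The number of valid values is reported per arm and per day.
- A sensitivity analysis uses the recorded NMB status and the 0800 mode.

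**Cost.** One tick per form and a few sentences in the SAP; patient care is unchanged. The price is fewer usable control values, and those that remain may come selectively from more heavily sedated patients. The counts per arm and day, together with the sensitivity analysis, are there to show how far that has gone.

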### 7.3/ 5.3 Blood Laboratory values data collection

Hematology (WBC, Hgb, Hct, Platelets), Chemistry (Potassium, Bicarbonate, BUN, Creatinine, Glucose, Magnesium, Phosphate, Albumin, Bilirubin AST/ALT results measured by standard of care and recorded as per study data collection requirements.

### 7.4/ Blood sugar

Blood sugar will be measured by fingerstick and analyzed with a handheld point-of-care glucometer (Accu-chek, Roche) and reported in the EMR by the nurse at the bedside who is not part of the study team.

### 7.5/ Fluid management

Fluid management of ARDS patients enrolled in the CHILL Study, excluding patient in shock, will follow clinical guidelines of conservative approach fluid management.

This conservative fluid management approach will represent a simplification of the algorithm utilized in the ARDS Network FACTT study . If not already being utilized, this conservative fluid management approach must be initiated within four hours of randomization and continued until the subject has reached unassisted breathing (UAB) or study day 7, whichever occurs first.

1. Discontinue maintenance fluids.
2. Continue medications and nutrition.
3. Manage electrolytes and blood products per usual practice.

4. For shock, use any combination of fluid boluses and vasopressor(s) to achieve mean arterial pressure  $\geq 60$ mm Hg as fast as possible.
  - Consider assessing for hypovolemia with bedside ultrasound (IVC collapsibility) and/or fluid responsiveness with passive leg raise (PLR) before bolusing fluid
  - Recommended fluid bolus = 15mL/kg crystalloid rounded to nearest 250 mL or 1 unit packed red cells or 25g albumin
  - Wean vasopressors as quickly as tolerated beginning 4hr after blood pressure has stabilized.
5. Withhold diuretic therapy in **renal failure** and until 12h after last fluid bolus or vasopressor use.
  - **Renal failure** defined as dialysis dependence, oliguria with serum creatinine  $> 3$ mg/dL, or oliguria with serum creatinine 0–3 with urinary indices indicative of acute kidney injury).

**Table 1: Guidelines for Fluid Management**

CVP a	PAOP (optional)	MAP $\geq 60$ mm Hg AND off vasopressors for $\geq 12$ h	
		Average urine output $< 0.5$ ml/kg/hr	Average urine output $\geq 0.5$ ml/kg/hr
$>8^b$	$> 12^b$	Furosemide e Reassess in 1h	Furosemide e Reassess in 4h
4-8 c	8-12 c	Give fluid bolus Reassess in 1h	No intervention Reassess in 4h
$< 4^d$	$< 8^d$		

aIf no central venous catheter (CVC), peripherally inserted central catheter (PICC), or pulmonary artery catheter (PAC, Swan-Ganz catheter), consider assessing volume status with ultrasound of IVC or NT-proBNP. If these assessments are normal, or not available, treat as euvolemic (CVP 4-8 or PAOP 8-12).

bIf no CVC, PICC, or PAC present, can substitute distended IVC on bedside ultrasound or elevated NT-proBNP (adjusted for age)

cIf no CVC, PICC, or PAC present, can substitute normal caliber IVC (neither distended nor collapsible) on bedside ultrasound or normal NT-proBNP (adjusted for age). If these assessments are unavailable consider this euvolemic.

dIf no CVC, PICC, or PAC present, can substitute collapsible IVC on bedside ultrasound

eRecommended Furosemide dosing = begin with 20 mg bolus or 3 mg / hr infusion or last known effective dose. Double each subsequent dose until goal achieved (oliguria reversal or intravascular pressure target) or maximum infusion rate of 24 mg / hr or 160 mg bolus reached. Do not exceed 620 mg/day. Also, if patient has heart failure, consider treatment with dobutamine.

Fluid intake and output (I/O) will be obtained from EMR and recorded per study data collection requirements. I/Os will be computed every 24 hours for 0800-0759.

